7.2.2 Other Assays or Procedures

If after sending the donor serum for HCV genotyping extra donor serum is available, a sample of the donor serum (minimum of 0.5cc), will be banked. This will be retained indefinitely in the event that the donor genotype testing requires repeating at any time. See below for sample handling and labeling details.

7.2.3 Specimen Preparation, Handling, and Storage

Deceased donor blood routinely accompanies organs for transplantation to enable any additional testing a recipient center may wish to perform. For this study, we will utilize donor serum for purposes of HCV genotyping, as outlined above in 7.2.1, because genotyping for HCV positive donors is not performed regularly by UNOS. Donor blood accompanying the lung will be received in a red top tube. The whole blood will be spun in a centrifuge at 2000rpm x 15 minutes at 4°C. Serum will be removed with a pipette and transferred to a cryovials either for storage, or for packaging and shipping to Quest Laboratories for HCV genotype testing. The sample sent to Quest Laboratories will be a minimum of 1mL serum and will be labeled with donor demographic data only, no recipient data. Per standard specimen handling protocols at

CONFIDENTIAL

Quest Diagnostics, residual samples will not be retained by Quest. Once results are finalized, Quest Diagnostics destroys samples they have tested.

The alternative option for donor blood processing (labeled with donor demographic data only, no recipient data) is having the NYU Laboratory process the samples via standard of care and providing the results to the research team.

The sample banked for storage will be labeled with the donor UNOS identification number (a unique transplant identifier that has no patient- derived identifiers), the recipient's study subject number, at the date collected. Banked samples will be stored in a -80°C freezer, located at [name].

See attached documents (Section 19) for detailed standard operating procedures for specimen processing, collection and shipping instructions from Quest Laboratories, as well as for the accreditation documentation for the Transplant Research Lab, where these specimens will be processed and stored. intolerances to Mavyret, due to illness associated with acute HCV infection, HCV resistances) will occur as clinically appropriate and any AEs/SAEs will be documented as described below.

Recipient blood will be processed at the NYU Laboratory while patient is hospitalized and will be processed in local laboratories (Quest, LabCorp) or NYU Laboratory while the patient is outpatient.

7.4 Concomitant Medications, Treatments, and Procedures

The subjects will receive concomitant medications, which would otherwise be given as standard of care for patients undergoing a lung transplant.

7.4.1 Precautionary Medications, Treatments, and Procedures

Treatment with amiodarone, digoxin, atorvastatin, lovastatin, simvastatin, pravastatin, rosuvastatin, flucastatin, pitavastatin requires special consideration and possible dosing adjustments in patients receiving Mavyret and the use of these medications will be discussed by the study team and any dose adjustment plan documented in the CRF.

7.5 Prohibited Medications, Treatments, and Procedures

Treatment with atazanavir, darunavir, lopinavir, ritonavir, efavirenz, rifampin, cyclosporine, ethinyl estradiol-containing oral contraceptives, carbamazepine, dabigatran, St. John's worth will not be permitted.

7.6 Rescue Medications, Treatments, and Procedures

In the event that a subject fails to achieve SVR with Mavyret, rescue therapy with other marketed agents approved for the treatment of HCV will be administered. The rescue treatment will be determined based on genotyping and resistance testing, and the choice of drug(s) used will be prescribed under the direction of a transplant hepatologist and/or transplant infectious diseases physician.

7.7 Participant Access to Study Agent at Study Closure

Not applicable

8 Assessment of Safety

8.1 Specification of Safety Parameters

CONFIDENTIAL

8.1.1 Definition of Adverse Events (AE)

An **adverse event** (AE) is any symptom, sign, illness or experience that develops or worsens in severity during the course of the study. Intercurrent illnesses or injuries should be regarded as adverse events.

For the purpose of this protocol an adverse event is any untoward medical occurrence in a clinical study subject associated with procedures required by this protocol in relation to Mavyret treatment.

An AE does not include the following for this study:

- Any medical condition or clinically significant laboratory abnormality with an onset date before the consent form is signed and before day 1 visit is not an AE.
- Any medical condition or clinically significant laboratory abnormality with an onset date after the consent form is signed that is not related to the study medication.

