8.1.2 Definition of Serious Adverse Events (SAE)

Serious Adverse Event

Adverse events are classified as serious or non-serious. A **serious adverse event** is any AE that is:

- fatal
- life-threatening
- requires or prolongs hospital stay
- results in persistent or significant disability or incapacity
- a congenital anomaly or birth defect
- an important medical event

Important medical events are those that may not be immediately life threatening, but are clearly of major clinical significance. They may jeopardize the subject, and may require intervention to prevent one of the other serious outcomes noted above. For example, drug overdose or abuse, a seizure that did not result in in-patient hospitalization or intensive treatment of bronchospasm in an emergency department would typically be considered serious.

All adverse events that do not meet any of the criteria for serious should be regarded as **non-serious adverse events**.

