8.2.2 Relationship to Study Agent

The clinician's assessment of an AE's relationship to study is part of the documentation process, but it is not a factor in determining what is or is not reported in the study. If there is any doubt as to whether a clinical observation is an AE, the event should be reported. All AEs must have their relationship to study agent assessed. In a clinical trial, the study product must always be suspect. To help assess, the following guidelines are used.

- **Related** – The AE is known to occur with the study agent, there is a reasonable possibility that the study agent caused the AE, or there is a temporal relationship between the study agent and event. Reasonable possibility means that there is evidence to suggest a causal relationship between the study agent and the AE.
- **Not Related** – There is not a reasonable possibility that the administration of the study agent caused the event, there is no temporal relationship between the study agent and event onset, or an alternate etiology has been established.

For all collected AEs, the clinician who examines and evaluates the participant will determine the AE's causality based on temporal relationship and his/her clinical judgment. The degree of certainty about causality will be graded using the categories below.

- **Definitely Related** – There is clear evidence to suggest a causal relationship, and other possible contributing factors can be ruled out. The clinical event, including an abnormal laboratory test result, occurs in a plausible time relationship to drug administration and cannot be explained by concurrent disease or other drugs or chemicals. The response to withdrawal of the drug (dechallenge) should be clinically plausible. The event must be pharmacologically or phenomenologically definitive, with use of a satisfactory rechallenge procedure if necessary.
- **Probably Related** – There is evidence to suggest a causal relationship, and the influence of other factors is unlikely. The clinical event, including an abnormal laboratory test result, occurs within a reasonable time after administration of the drug, is unlikely to be attributed to concurrent disease or other drugs or chemicals, and follows a clinically reasonable response on withdrawal (dechallenge). Rechallenge information is not required to fulfill this definition.

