8.3 Time Period and Frequency for Event Assessment and Follow-Up

The occurrence of an AE or SAE may come to the attention of study personnel during study visits and interviews of a study participant presenting for medical care, or upon review by the DSMB. All AEs including local and systemic reactions meeting the criteria for SAEs will be captured on the appropriate CRF. Information to be collected includes event description, time of onset, clinician's assessment of severity, relationship to study product (assessed only by those with the training and authority to make a diagnosis), and time of resolution/stabilization of the event. All SAEs occurring while on study must be documented appropriately regardless of relationship. All SAEs will be followed to adequate resolution.

Any medical condition that is present at the time that the participant is screened will be considered as baseline and not reported as an AE. However, if the study participant's condition deteriorates at any time during the study, it will be recorded as an AE. UPs will be recorded in the data collection system throughout the study.

Changes in the severity of an SAE will be documented to allow an assessment of the duration of the event at each level of severity to be performed. SAEs characterized as intermittent require documentation of onset and duration of each episode.

The PI will record all reportable events with start dates occurring any time after informed consent is obtained until 30 days (for SAEs) after the last day of study participation. At each study visit, the investigator will inquire about the occurrence of SAEs since the last visit. Events will be followed for outcome information until resolution or stabilization.

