8.4 Reporting Procedures – Notifying the IRB

8.4.1 Adverse Event Reporting

All AEs will be recorded in AE CRFs by a member of the study team. AEs will be recorded within 3 business days of the study team being made aware of the AE. The relationship of the AE to the study interventions will be noted by the PI. AEs that are deemed definitely related or probably related to the study interventions will be reported to the IRB and the DSMB within 3 days of their designation as such. The DSMB will determine the need for an emergency meeting between the DSMB and the study team (see

CONFIDENTIAL

safety oversight below). AEs that are deemed unrelated or not likely related to the study interventions will be recorded on CRFs as described above and will be reviewed at quarterly DSMB safety review meetings, and at annual review by the IRB.

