8.4.2 Serious Adverse Event Reporting

All SAEs will be recorded in SAE CRFs by a member of the study team. SAEs will be recorded within 3 business days of the study team being made aware of the SAE. The relationship of the SAE to the study interventions will be noted by the PI. SAEs that are both unexpected and deemed related to the study interventions will be reported to the IRB and the DSMB within 24 hours of the PI designation as such. The DSMB will determine the need for an emergency meeting between the DSMB and the study team (see safety oversight below) or whether these can be reviewed at quarterly meetings. SAEs that are deemed unrelated or not likely related to the study interventions will be recorded on CRFs, will be reported to IRB and DSMB within 3 days of their designation as such and will be reviewed at quarterly DSMB safety meetings.

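### Section 8.1.1 ties adverse events to Mavyret, contradicting five other statements in the plan, so non-fatal harm from donor-derived HCV could be left out

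*Combined protocol and SAP*

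**What the plan says.** Section 8.1.1 opens broadly. Any symptom or illness that arises or worsens on study is an adverse event (AE), and "Intercurrent illnesses or injuries should be regarded as adverse events". A protocol-specific sentence then narrows this to occurrences "associated with procedures required by this protocol in relation to Mavyret treatment". The last exclusion bullet goes further and removes any medical condition or any "clinically significant laboratory abnormality with an onset date after the consent form is signed that is not related to the study medication".

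Section 8.1.2 builds seriousness on that definition: "Adverse events are classified as serious or non-serious".

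Other sections take the opposite line on relationship:
- 8.2.2 says that the clinician's assessment of relationship is documented, "but it is not a factor in determining what is or is not reported in the study".
- 8.3: "All SAEs occurring while on study must be documented appropriately regardless of relationship".
- 8.4.1: "AEs that are deemed unrelated or not likely related to the study interventions will be recorded on CRFs".
- 8.4.2: "SAEs that are deemed unrelated or not likely related to the study interventions will be recorded on CRFs".

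Section 8.5 lists three grounds for halting enrollment: a death related to the intervention, a serious adverse event (SAE) related to acute HCV infection, and an SAE related to Mavyret.

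**The concern.** The primary objective (3.1) is the safety and efficacy of transplanting lungs from HCV-positive donors into HCV-negative recipients. The safety of Mavyret is only part of that. The harm particular to this strategy is HCV infection from the donor organ, and an illness caused by the virus need not be related to the drug. A definition that turns on relation to the drug can therefore drop the events the study exists to observe.

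Two things are at stake. First, two coordinators working from different sections could record different events for the same patient. Second, an HCV-related SAE is a halting ground, but if an event fails the AE definition it has no clear route to being called an SAE.

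**Working it through.** No arithmetic applies: the point rests on no rate, sample size or power figure. The check takes one test case through each section. The case is a non-fatal hepatitis from donor-derived acute HCV that the clinician judges not to be due to Mavyret.

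| Section | Rule | Result for the test case |
|---|---|---|
| 8.1.1, first paragraph | New or worsening illness counts, intercurrent illness included | AE |
| 8.1.1, protocol-specific sentence | Must be tied to protocol procedures concerning Mavyret | Not an AE |
| 8.1.1, last exclusion bullet | Not related to the study medication means excluded | Not an AE |
| 8.2.2 | Relationship does not decide what is reported | Reported |
| 8.3 | All SAEs documented whatever the relationship | Documented if serious |
| 8.4.1 | Unrelated AEs go on the case report form (CRF) | Recorded |
| 8.4.2 | Unrelated SAEs go on the CRF, and to the IRB and DSMB within 3 days | Recorded and reported if serious |
| 8.5 | An HCV-related SAE halts enrollment | Halts if serious |

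1. **Contradiction.** The two restrictive statements in 8.1.1 cannot be reconciled with the five statements from the first paragraph of 8.1.1, 8.2.2, 8.3, 8.4.1 and 8.4.2. If relation to Mavyret is part of being an AE, the procedures for unrelated AEs and SAEs have almost nothing to apply to.

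2. **Effect on SAEs.** Under 8.1.2 an SAE is an AE that meets a seriousness criterion. An event that 8.1.1 excludes is therefore not an SAE on that wording, and the second ground in 8.5 is undercut for it.

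3. **What does not depend on 8.1.1.** The halt for any death (10.4.6.1) and the halt for treatment failure (10.4.2) do not use the AE definition. The Mavyret-related SAE ground in 8.5 survives because such an event passes the exclusion bullet. Unanticipated problems (8.1.3) are defined without the term AE. That route is only partial cover: it requires the event to be unexpected, and acute HCV is already described in 2.4.1. Of the three grounds in 8.5, one is affected.

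4. **Which relationship is graded.** Section 8.2.2 grades relationship to the study agent, and 8.4.1 and 8.4.2 refer to the study interventions. None of them asks for relationship to HCV infection, which is the judgement the second ground in 8.5 needs.

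5. **Planned summaries.** The list in 10.4.1 covers viremia, clearance, treatment failure and genotype, and 10.4.3 adds survival. The 10.3 dataset names demographic and HCV test data. No AE or SAE summary is named in section 10.

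**The case against.** The strongest reply is that the intent is plain. Section 8.5 names an HCV-related SAE as a halting ground. A cut-off sentence at the end of 7.2.3 also mentions illness from acute HCV infection alongside documentation of AEs and SAEs. Staff following 8.3 and 8.4 would record these events. This stands as evidence of intent and limits the practical effect, but it does not make 8.1.1 correct.

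A reader might infer that the HCV halting ground can never operate. The documents do not support that. Section 8.2.2 counts a temporal relationship as a basis for calling an event related and tells the clinician always to suspect the study product. Mavyret starts once viremia is detected, so an HCV illness on treatment could be graded related and pass the exclusion bullet. The same section lets an established alternative cause make the event unrelated, so the outcome is ambiguous.

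A reader might also infer from section 10 that safety would go unreported. That too goes beyond the text. The 10.4.1 list is not stated to be exhaustive, 14.1 has AEs collected, 8.6 has the DSMB review cumulative safety data quarterly, and 4.2.1 and 4.2.2 assess the risks through SVR, survival and viremia. The missing table is a secondary point of detail.

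**Conclusion.** The definition in 8.1.1 is wrong as written and should be corrected. One sentence and one bullet conflict with five other statements and weaken one of the three halting grounds in 8.5.

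The exposure is limited to non-fatal HCV-related or other strategy-related events that are judged unrelated to Mavyret, and it arises only if staff apply 8.1.1 over 8.3, 8.4 and 8.5. No probability that the halting ground is missed is claimed: the documents give no rate of HCV-related SAEs and do not say which section prevails.

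The text available for review lacks 7.2.4 to 7.3.6, the DSMB charter and the manual of procedures. Nothing is concluded about them.

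**What to change.** In 8.1.1, delete the whole protocol-specific sentence (the second paragraph) and the last exclusion bullet, so that any untoward event after consent is an AE whatever its relationship. Striking only the reference to Mavyret from that sentence would not be enough, because AEs would still be limited to events tied to protocol procedures.

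On the AE and SAE CRFs, grade relationship to Mavyret and to HCV infection separately, so that the SAE grounds in 8.5 can be read directly from the form.

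Optional and secondary: add to 10.4.1 a listing of AEs and SAEs for all transplanted recipients, by seriousness and relationship.

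The cost is two deletions, one further relationship field and, if wanted, one listing for 20 patients, with IRB approval of the amendment under 13.2. No new tests are needed. The downside is that more post-transplant events would be recorded, and unrelated SAEs would go to the IRB and DSMB within 3 days. Sections 8.3, 8.4.1 and 8.4.2 already ask for that recording and reporting.

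### Section 8.1.1 counts only Mavyret-related events as adverse events, contradicting its own opening and sections 8.2.2, 8.3, 8.4.1, 8.4.2 and 8.5

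*Combined protocol and SAP*

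**What the plan says.** Section 8.1.1 of the combined protocol and SAP holds two definitions. The opening one is broad: "Intercurrent illnesses or injuries should be regarded as adverse events". The one specific to this protocol is limited to occurrences "associated with procedures required by this protocol in relation to Mavyret treatment". The second exclusion bullet then removes clinical conditions and significant laboratory findings that have "an onset date after the consent form is signed that is not related to the study medication". Section 8.1.2 builds on this, because a serious adverse event "is any AE that is" fatal, life-threatening or otherwise on its list.

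Other sections point the other way:

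- 8.2.2, on the clinician's causality assessment: "it is not a factor in determining what is or is not reported in the study". It adds: "If there is any doubt as to whether a clinical observation is an AE, the event should be reported".
- 8.3: "All SAEs occurring while on study must be documented appropriately regardless of relationship". If the participant's condition "deteriorates at any time during the study, it will be recorded as an AE". The inquiry it sets for each visit, however, is about SAEs only.
- 8.4.1 has all AEs entered on CRFs and includes a rule for those judged unrelated to the study interventions. 8.4.2 does the same for SAEs.
- 8.5 lists an SAE attributed to acute HCV infection as a reason to halt enrolment, separately from one attributed to Mavyret.

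The primary objective (3.1) is the safety and efficacy of transplanting lungs from HCV-positive donors with subsequent anti-HCV therapy.

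**The concern.** The strategy brings three hazards: the drug, donor-derived HCV and the donor organ. The protocol-specific definition admits only the first, although the primary objective covers all three. The narrow wording is also the one labelled as applying to this protocol, so staff could reasonably treat it as the working rule.

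Staff who follow 8.1.1 would leave an HCV-caused event off the AE form. Staff who follow 8.4.1 would enter it. What the DSMB sees at its quarterly reviews would then depend on which section was used. A single-arm pilot has no control group against which such a gap would show up.

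**Working it through.** The plan states no figure on this point, so the check is a comparison of text. Two cases are taken through the sections. In case A, a recipient has a positive HCV PCR and a non-serious but clinically significant ALT rise before the first Mavyret dose. ALT is among the tests reviewed under 7.2.1, and 2.1 and the Section 19 footnote start Mavyret only once virus is detected. In case B, the same HCV illness prolongs the hospital stay.

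| Section | Case A (non-serious) | Case B (serious) |
|---|---|---|
| 8.1.1, opening | AE | AE |
| 8.1.1, protocol-specific sentence | Not an AE | Not an AE |
| 8.1.1, second exclusion bullet | Not an AE; laboratory findings are named | Not an AE |
| 8.1.2 | Not relevant | Not an SAE, because not an AE |
| 8.2.2 | Report | Report |
| 8.3, recording | AE, if read as a deterioration | Document, whatever the cause |
| 8.3, visit inquiry | Not asked about | Asked about |
| 8.4.1 / 8.4.2 | Record, if it counts as an AE | Record |
| 8.5 | No role | Halts enrolment |

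**Case B.** The literal chain from 8.1.1 to 8.1.2 would drop the event. The all-SAE rule in 8.3, the recording rule in 8.4.2 and the HCV trigger in 8.5 override it in plain terms. Serious events are therefore protected.

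**Case A.** The protection is partial. The doubt rule in 8.2.2 applies to any clinical observation, but it needs doubt, and someone reading only the exclusion bullet may have none. Section 8.4.1 covers all AEs, which leads back to the definition. Its clause on unrelated AEs does imply that such events count. No visit question in 8.3 would bring the event up.

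**Fragment at the end of 7.2.3.** In the text available, this section runs into a fragment that apparently belongs to 7.3. It mentions illness from acute HCV infection and says that AEs and SAEs will be documented as set out further on. This shows an intention to capture such events, but it sends the reader to section 8, where the conflict lies.

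**Unanticipated problems (8.1.3).** This route is no substitute. It requires an unexpected event, and 2.4.1 already describes acute HCV as a known risk.

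**Attribution.** Section 8.2.2 grades relationship to the study agent only. Sections 8.4.1 and 8.4.2 speak of study interventions, and 8.5 needs a judgement on HCV. No grading is given for relatedness to HCV or to the donor organ.

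**Effect on analyses.** The endpoints in 4.2 are SVR, one-year survival and incidence of viremia. The descriptive statistics in 10.4.1 cover viremia, clearance, treatment failure and genotype. None is an AE count, and all are collected whatever 8.1.1 says.

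**The case against.** The strongest reply is that the document, read as a whole, already settles the matter. If the exclusion bullet governed, the clause in 8.4.1 on unrelated AEs would have nothing to act on, and a reading that empties a clause is a poor one. The doubt rule in 8.2.2 is not limited to serious events. The fragment after 7.2.3 names AEs, not only SAEs, in connection with HCV illness. Survival, viremia and SVR do not pass through the AE definition.

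Much of this stands. It shows what the authors probably meant, and it confines the problem to non-serious events outside the endpoints. It does not make 8.1.1 correct, since the sentence labelled as specific to the protocol still says the opposite.

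A second reply also stands. Deleting the limits without further provision would bring in routine post-transplant complications. Section 19 lists the operation among the study-specific interventions, although the Protocol Summary names only treatment and surveillance. On the Section 19 reading, 8.4.1 would send surgical AEs judged definitely or probably related to the IRB and DSMB within 3 days. The fix has to prevent that.

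A reader might infer that serious HCV-related events would be lost. Sections 8.3, 8.4.2 and 8.5 do not support that. A reader might also take the time patients spend off Mavyret, or the number never treated, as the size of the loss. Neither measures events. If treatment starts on viremia, recipients never treated are those in whom no viremia was detected, so they say little about lost HCV events. With PCR at each week from POW1 to POW12, the viremic period before the first dose should be short in that phase.

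**Conclusion.** The definition in 8.1.1 is wrong as written and should be corrected. It contradicts its own opening and 8.2.2, 8.3, 8.4.1, 8.4.2 and 8.5, and it is too narrow for the primary objective.

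The consequence is limited to inconsistent recording of non-serious events related to HCV or the donor organ in the DSMB's safety data, in at most 20 patients. No endpoint result changes. The number of events affected cannot be estimated from the documents.

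This rests on three conditions. First, some staff would apply 8.1.1 literally. Second, Mavyret starts on detection of virus; if the statement in 2.4.1 that all patients are treated from transplant governs instead, the ALT example before the first dose falls away, but the exclusion of events not caused by the drug remains. Third, the visit text of 7.3 is absent from the text reviewed and may already include an AE inquiry. That would close the gap in 8.3 but would not resolve the conflict in 8.1.1.

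**What to change.** 1. In 8.1.1, delete the sentence that limits AEs to Mavyret and the second exclusion bullet, leaving the broad opening definition.
2. On the CRF, record relatedness to Mavyret, to HCV infection and to the donor organ or transplant as separate items.
3. In 8.3, have the visit inquiry cover AEs and SAEs, unless 7.3 already does so.
4. State that expected non-serious transplant complications are recorded but exempt from the 3-day reporting in 8.4.1.

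The cost is a text amendment and the added attribution items on the CRF. The change asks for no recording beyond what 8.4.1 and 8.4.2 already call for. A team that has worked to the letter of 8.1.1 would record somewhat more, mainly non-serious post-transplant complications in up to 20 patients.
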